#### **Data Collected**

All data collected will be entered into a Redcap database for analysis. All collected data will be de-identified and samples will only have a unique identifier that will link the unique identifier with the patient's name.

Results of the COWS and pain VAS scores, OCS and CNSVS assessments at the respective time points will be tabulated and analyzed.

Upon completion of each patient's treatment with the device (sham or active), patients will be asked if they thought they had an active or inactive device. They will also be asked to respond to the questions: Do you want an active, functioning device to be placed prior to going home today (yes/no)? and on a 7 point Likert scale: 1) "How useful do you think the BRIDGE Device was for you overall in your treatment?" 2) "What is your impression of the effectiveness of the BRIDGE Device to treat your symptoms of withdrawal?" 3) "How satisfied are you and how the BRIDGE device worked for you?" and 4) "How likely are you to use the device again if you have symptoms of withdrawal?" Results will be tabulated and analyzed descriptively.

Analysis will also include differences in dosing of buprenorphine as well as usage of other symptom control medications and continued engagement in recovery treatment at 5- and 30-days post-device placement. If subject does not return to clinic at the 5- and 30-day scheduled appointment as dictated by clinic standard practice, a phone call will be made to assess whether the patient is still engaged in a recovery program.

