### DATA MANAGEMENT

#### GENERAL CONSIDERATIONS FOR DATA ANALYSES

In general, for demographics, baseline disease characteristics, type of opioid misused, and all safety data, continuous variables will be summarized using descriptive statistics including N, mean, median, standard deviation (SD), minimum, and maximum. For all the efficacy parameters (e.g. COWS, VAS, OCS and CNSV experience with the device, continued engagement in recovery program) the descriptive statistics will include N, mean median, standard error (SE), minimum and maximum or percentage and exact Clopper Pearson 95% confidence interval.

**Definition of analysis population** Intent-to-treat (ITT) Population The intent-to-treat (ITT) population will include every subject who is randomized to a treatment assignment (BRIDGE or Sham). The ITT population will be the primary population for all efficacy analyses and will be the basis of all sensitivity analysis.

Patients who received study medication different from that to which they are randomized will be included in the group to which they are randomized. All data will be analyzed by randomized treatment group.

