#### **Safety Population**

The safety population will consist of all patients who have received at least one hour of treatment. The safety population will be used for analysis of all safety data.

Patients who received study treatment different from that to which they were randomized will be included in the group according to the treatment actually used.

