#### Adverse Events

All adverse events will be summarized for the following 3 study periods separately, and include the specified AEs:

• Screening Period: Include the AEs of which the onset date is before the start of the study device placement.

• Treatment Period: Include (a) the AEs of which onset date is on or after the first day of the study device and on or prior to five days after the last device treatment day.

• Follow-up Period: Include (a) the AEs of which onset date is more than 30 days after the last device placement; OR (b) the AEs of which onset date is during the treatment period with the end date is more than 30 days after the last dose day or is unresolved and the follow up intensity is worse than the initial intensity.

For each AE recorded, the term entered by the investigator describing the event (the "verbatim term") will be assigned to a standardized term (the "preferred term") based on the Medical Dictionary for Regulatory Activities (MedDRA) dictionary. Within this dictionary, all preferred terms are grouped into categories known as "system organ class" terms or "super class" terms (SCT). All data displays of AE will be performed using the preferred terms and super-class terms (also referred as Body System).

For each treatment group, the frequency of each AE preferred term will be defined as the number of patients reporting at least one occurrence of the event. The incidence rate will be calculated as the frequency count divided by the total number of patients in the population and treatment group specified. Each table will also present the overall number of patients experiencing at least one AE and the total number of adverse events reported.

In the summary table of AEs by intensity, if a patient has more than one occurrence of an event, the event with the most severe intensity will be counted. If the intensity of an adverse event is missing, then the AE will be included only in the total number of events columns, and not in the count of patients with the event by intensity. In the summary table of AEs by relationship to trial treatment, if a patient has more than one occurrence of an event, the most closely related event will be counted. If the relationship of an adverse event is missing, then the AE will be included only in the total number of events columns, and not in the count of patients with the event by relationship.

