#### Safety Monitoring Plan

All procedures will be performed by trained professionals within the standard of care under continuous medical supervision while in the outpatient clinic. Potential side effects will be documented as noted above. COWS score ratings will be filled out by nursing staff or provider as per standard of care. All patients will be carefully monitored. If any serious harm or discomfort is identified by the subjects or the study personnel, the treatment will be discontinued. Any patient with worsening or no improvement in symptoms who has a device placed during the study will be able to drop out at any time and receive standard of care medical therapy. The skin of the external ear will be carefully monitored for signs of irritation or infection. All patients will be given the option to have an active device at the end of the 5 day study period at no cost.

Safety Analysis Plan

There are no dangerous interventions related to this study.

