#### **Demographic Information**

Data will be collected as part of the clinic visit. This includes subject's date of birth, age, sex and ethnicity. The physician assessment will also include questions about prior medical diagnoses, co-morbid symptoms and the characteristics of the current illness. Types of illicit drugs used other than opioids (benzos, alcohol, etc.), duration of drug use, underlying psychiatric disorders.

Efficacy Information

- 1. Clinical Opioid Withdrawal Scale (COWS) (total time 5 min)
- 2. Pain (11-point VAS) (total time 2 min)
- 3. Opioid Craving Scale (11-point scale) (total time 3 min)

a. How much do you currently crave opiates (Range: 0-10, 0 = not at all, 10 = extremely)

b. In the past week, please rate how strong your desire to use opiates has been when something in the environment has reminded you of opiates (examples: seeing a medication bottle, using the Internet, visiting a doctor's office, going to a place where you used to buy drugs)? (Range: 0-10, 0 = not at all, 10 = extremely)

c. Please imagine yourself in the environment in which you previously used opiates (examples: a party, a hangout, a particular room where you live). If you were in this environment today and if it were the time

of day that you typically used opiates, what is the likelihood that you would use opiates today? (Range: 0-10, 0 = not at all, 10 = extremely)

- 4. CNS Vital Signs in-office neurocognitive testing with domain scores (total time 15 min). https://www.cnsvs.com/index.html
- 5. Four question patient questionnaires at end of study period
- 6. Dosing of medication assisted therapy (buprenorphine)
- 7. Additional (symptom control) medication log
- 8. Number of subjects with continued engagement in recovery treatment at 5 days post-device placement
- 9. Whether the patient thinks they had an active or inactive device at end of 5 days treatment

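### Both arms may take a free active device at the end of Day 5, and the plan has no rule for later data, so Day 30 engagement and later by-arm adverse events are not active versus sham

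*Combined protocol and SAP*

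**What the plan says.** - **Offer.** The Safety Monitoring Plan says: "All patients will be given the option to have an active device at the end of the 5 day study period at no cost". Under Data Collected, each patient is asked on completing the randomised device whether they want a working one fitted before leaving that day. Both arms are asked.
- **Engagement.** Data Collected plans to analyse differences in "continued engagement in recovery treatment at 5- and 30-days post-device placement". The general considerations for analysis list "experience with the device, continued engagement in recovery program" among the efficacy parameters, and the ITT definition adds: "All data will be analyzed by randomized treatment group". Item 8 of the efficacy information is narrower: "Number of subjects with continued engagement in recovery treatment at 5 days post-device placement".
- **Adverse events.** The Safety Analysis section summarises safety by treatment group and period, follow-up included. The Adverse Events section ends the treatment period "on or prior to five days after the last device treatment day" and starts follow-up more than 30 days after the last device placement.
- **Safety grouping.** Patients who received something other than their randomised treatment "will be included in the group according to the treatment actually used".
- **What is absent.** No section says how data after the offer are analysed, or whether an open-label device counts as the last device in the AE definitions. The wish for a device is recorded, and the placement steps log device serial numbers, but the listed data do not include actual placement of a second device or its date.

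**The concern.** From the end of Day 5 a sham patient may wear the active device. A by-arm engagement result at Day 30 could then be read as the effect of active versus sham on retention, when both arms had access to active stimulation for most of that month. Retention is a claimed benefit in the protocol's statement of significance, and Day 30 is its latest named engagement time point, so a small or null difference there would be hard to interpret. The AE tables have a similar problem: events from an open-label active device would stand in the sham column with nothing to separate them. If uptake and placement dates are not recorded during the trial, neither can be sorted out afterwards.

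**Working it through.** **Plan's own figure.** The only power statement concerns one-hour COWS: 25 per arm, 0.94 SD, two-sided alpha 0.049, at least 90%. A noncentral t calculation with 48 degrees of freedom gives 90.1%, so it reproduces. It precedes the offer and is unaffected. The plan gives no power or expected rate for engagement and no expected uptake, so the engagement figures below are illustrations.

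**Timeline.** The randomised device is worn to Day 5. If that is the last device treatment day, the AE treatment period ends at Day 5 + 5 = Day 10. An open-label device fitted on Day 5 and worn for five days (wear time assumed equal to the randomised device) falls inside that window. If the open-label device counts as the last device, the window runs to about Day 10 + 5 = Day 15. On either reading those AEs fall in the by-arm treatment period. Events that persist or start late can also reach the follow-up table.

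**Day 30 engagement.** Let Δ be the difference with no open-label use, u the sham uptake, g the share of Δ that a late device gives a sham acceptor, v the active-arm uptake, and h the gain from repeat wear. Then

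observed difference = Δ(1 − u·g) + v·h.

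With assumed engagement of 50% sham and 70% active (Δ = 20 points) and h = 0:

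| Sham uptake u | g = 1: difference (power) | g = 0.5: difference (power) |
|---|---|---|
| 0% | 20 (30%) | 20 (30%) |
| 25% | 15 (19%) | 17.5 (24%) |
| 50% | 10 (11%) | 15 (19%) |
| 100% | 0 | 10 (11%) |

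Power is for 25 per arm, two-sided 0.05. At g = 0 the difference stays at 20 whatever the uptake. If active-arm patients also accept and gain, part is restored: u = v = 50%, g = 1 and h = 10 points gives 20 − 10 + 5 = 15. The difference shrinks only if u·g·Δ exceeds v·h.

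**AE counts.** The adverse event section puts each listed risk at 1% to <5%. If 60% of 25 sham patients accept (assumed), there are 15 placements and 15 × 0.01 = 0.15 to 15 × 0.05 = 0.75 expected events per type.

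**AE contrast.** Let s and a be the per-wear risks for sham and active. With equal uptake u in both arms, the cumulative sham risk is 1 − (1 − s)(1 − u·a), the active risk is 1 − (1 − a)(1 − u·a), and their difference is (a − s)(1 − u·a). For assumed s = 1% and a = 5%:
- u = 0: 1.0% versus 5.0%, a difference of 4.0 points.
- u = 50%: 3.5% versus 7.4%, a difference of 3.9 points.
- If only sham patients accept at 50%: 3.5% versus 5.0%, a difference of about 1.5 points.

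The distortion therefore depends mainly on whether uptake differs by arm.

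**The case against.** The case for leaving this alone is substantial. Engagement is in neither specific aim and has no named test or power; the plan gives percentages with exact intervals. Item 8 of the efficacy information already lists Day 5 only. The wish for a device is already recorded. All of this limits the stakes, but none of it supplies a rule for data after the offer.

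A reader might also infer more than the documents support:

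- **That Day 30 is invalid.** It is not. By randomised arm it compares five days of active with five days of sham, each followed by an optional active device. The plan simply does not say that this is the question.
- **That the result is certainly biased toward zero, in proportion to uptake.** A 20-point difference falling to 12, 8 or 4 at 40%, 60% or 80% uptake needs g = 1 and no gain from repeat wear in the active arm. The first sits badly with the protocol's rationale, which places most first-month dropout in the first week. Placement is also offered at a clinic visit, and patients who cannot attend on Day 5 remove the device at home, so sham patients already lost would mostly not receive one. Those figures are near a worst case.
- **That sham completers move to the active column.** The as-treated rule covers patients who received something other than their randomised treatment. A patient who completed sham and then took the offer received sham as randomised, so moving them is a strained reading.
- **That the AE tables will materially flatter the device.** Few events are expected, several listed risks arise from needles or adhesive and not from current, and active-arm acceptors add events to their own column.

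**Conclusion.** The gap is real and of modest size. The plan analyses engagement at Day 30 by arm, and AEs beyond Day 5 by arm, without any rule for a device that both arms may take at the end of Day 5. Day 30 is a valid comparison of initial assignment with optional active device; it should not be reported as active versus sham. Whether and how far the engagement difference shrinks depends on uptake and benefit in each arm, none of which the documents give; at zero uptake nothing changes. Under the stated rules, open-label AEs in sham patients are counted under sham from about Day 5 to Day 10 and in follow-up, with roughly 0.15 to 0.75 events per type expected on the assumption of 15 placements. The primary endpoint, Day 5 engagement if recorded before the offer, and the other assessments made before the offer are untouched.

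**What to change.** Leave the offer as it is and change the analysis and data capture:

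1. Make Day 5 engagement, recorded before the offer, the active-versus-sham comparison, consistent with item 8 of the efficacy information. Report Day 30 as initial assignment with optional active device, show uptake by arm, and reconcile the two sections on whether Day 30 is an outcome.
2. End the randomised by-arm AE comparison at one common point for all patients: the end of the randomised device period, before any open-label placement. Tabulate later AEs separately by randomised arm and open-label uptake. Do not close the window patient by patient at open-label placement: follow-up would then depend on a choice made after randomisation, while the incidence denominators remain counts of patients.
3. Record whether an open-label device was actually placed, and the date.

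If any data after Day 5 enter the repeated-measures model, which mentions a horizon of up to three months, the same separation should apply.

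The cost is a few sentences in the analysis plan and an added case report form entry for placement and date. The price is a weaker Day 30 claim and a shorter by-arm AE window.

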# TOTAL NUMBER OF HUMAN RESEARCH PARTICIPANTS PROPOSED FOR THIS STUDY AT THIS SITE.

A total of 50 subjects will be recruited for this study. Stopping points for the study include achieving adequate information on sufficient study subjects, unanticipated adverse events, inability to obtain enough data or patients/caregivers electing to discontinue the study.

#### Power Calculation for primary aim (difference in COWS scores between active and sham device).

We hypothesize that compared to sham treatment, the improvement in COWS due to the BRIDGE device will be significantly higher than the sham. Similarly, pain and craving as measured by the VAS and OCS will be reduced. Patients with the active BRIDGE device will have improved memory and executive function compared to sham as assessed by CNSVS.

The primary outcome is comparison of change from baseline of the COWS scores between active and sham device at one hour. The data will be analyzed as a randomized, placebo-controlled trial with an interim analysis when 24 patients are completed at a P< 0.001. We will compare the bridge device and sham using a two sided t-test of the change of COWS at one hour form baseline. Using the sample size software Pass 15 with 25 subjects in each group we will have at least 90% power at an alpha of 0.049 to detect a difference in the COWS at one hour between treatment and sham of at least .94 standard deviations(SD), In the withdrawal study we had a SD of ~6, and so if we have a similar variability we will be able to detect a difference of approximately 5.7 (1). In the paper, we found a difference of > 12, so even allowing for a placebo effect we should have adequate power.

Period	Baseline	(1-hour after BRIDGE)	(1-hour after BUP)	Post- MAT	Post- MAT	Post- MAT	Post- MAT
Contact	Clinic	Clinic	Clinic	Phone	Phone	Phone	Clinic
Project Day	1	1	1	2	3	4	5
Informed Consent	Х						
Demographics and Medical History	Х						
Prior and Concomitant Medications	Х						х
Vital Signs, height, weight and BMI	х						
Physical Examination	Х						
Placement of BRIDGE Device or sham	Х						
COWS scores	Х	х	Х	х			х
VAS pain and craving scale	Х	х	Х	Х	х	Х	Х
Neurocognitive assessment	Х	x					Х
First dose of Buprenorphine		Х					

#### **DEVICE PLACEMENT PROCEDURE**

#### Auricular Neurostimulation treatment protocol

The electrode/needle arrays are placed according to the individual's distribution of neurovascular bundles. The exact location of the placement may vary slightly from person to person but is determined by both knowledge of auricular neuro-anatomy and visualization of the neurovascular bundles by transillumination. The points will be targeted by four-point electrical stimulation after carefully disinfecting the ear. The generator/battery will be positioned and secured behind the ear (similar to a hearing aid) and may be covered by hair. Neurostimulation in active devices will be delivered for 5 consecutive days. The device will be applied by a trained MD or APN and will be removed during the clinic visit or independently at home. The devices are easily removed by removing the tapes and adhesives.

The NSS-2 BRIDGE Surgical kit consists of:

- (1) An alcohol swab (2) prep and stay swab (3) round fixation plasters
- (4) fixation plasters to fasten the generator (5) Steri-strip adhesive vial
- (6) Sterile wire harness pack (7) Generator (8) Tweezers (9) Surgical marker (10) Transilluminator (Figure 5).

#### NSS-2 BRIDGE placement details:

- 1. A research coordinator will document the patient ID, name and the device serial number in the study database.
- 2. The research coordinator or provider will record baseline answers to questionnaires and will also record vital signs (temperature, heart rate and blood pressure).
- 3. The neurostimulator placement will be performed as directed and per BRIDGE training protocol instructions identical to prior IRB approved protocols.

- 4. Before device placement, the subject caretakers should be advised that some discomfort is normal at first. If the discomfort persists or worsens after a few minutes the medical provider will be notified. The patients will be advised that they may feel a slight pulsing sensation and perhaps a warming sensation in the ear to which the electrodes are affixed. The pulsing and warming sensation may disappear after approximately 5 minutes. If the discomfort level increases the offending array can be repositioned until the patient's discomfort level decreases to an acceptable level.
- 5. Subjects will be advised not to immerse the device in water as the device is water resistant but not water proof. If showering or washing their hair, placing a dry wash cloth over the area to help protect the device will be recommended. Subjects will be given a contact person (Principal investigator, Co-investigator or Research coordinator) to call if they are having any problems with the device or if it falls off.
- 6. The device may be removed by the patient or a caretaker if at home. If uncomfortable doing so or unable to carry out the instructions, an outpatient appointment will be made and the device will be removed by the investigators.
- 7. If removed at home, the patient will be asked to return the used device for proper disposal when they return the following week.

#### Figure 5

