#### **DESIGN AND METHODS**

The study will recruit a total of 50 subjects and will take place in a well-established outpatient treatment center (Brightview). Brightview is a private addiction treatment center located in Cincinnati, Ohio. The site PI at Brightview will be [name] [name] (MD, ABIM, ABAM DABPM), a board-certified physician in addiction medicine. [name] (PhD) will be a Co-investigator. The volume of patients treated for opioid use disorder (OUD) at this facility is sufficient for patient recruitment in this study. [name] will be responsible for patient recruitment and overseeing the entire project at Brightview. He will monitor the health of all patients in the study per standard clinical practice. [name] will be responsible for patient recruitment as well and monitor protocol adherence as well as supervise data collection, entry, and analysis.

This study will involve a double-blind, randomized, controlled trial with active BRIDGE or sham device (Figure 3). The sham device will be identical in appearance to the active device but will have no electrical current. Both providers and patients will be blinded to treatment allocation throughout the study. Participants will be 18 years or older who speak English and meet criteria for opioid use disorder based on the Diagnostic and Statistical Manual of Mental Disorders-5. Patients going through acute opioid withdrawal will be assessed for the severity of opioid withdrawal using the Clinical Opioid Withdrawal Scale (COWS). Additional demographic data will be collected at presentation including age, sex, duration of opioid misuse, types of medications or illicit drugs used as well as the presence of other medical conditions. After the severity of opioid withdrawal is established (COWS score  $\geq 10$ ), subjects will be randomized in blinded fashion. Once the patient is consented, a visual analog scale (VAS) for pain and an opioid craving scale (OCS) will be completed. Baseline cognitive function will be measured with the Stroop test using the CNS Vital Signs (CNSVS) in-office neurocognitive testing software https://www.cnsvs.com/index.html. This instrument measures executive function. The test takes approximately

4 minutes to administer and will be performed at the same intervals as COWS score, pain and craving assessments before and after device placement.

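### The advice on ear sensation risks unblinding patients before the 1-hour primary COWS, and no planned data can show whether the blind held then

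*Combined protocol and SAP*

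**What the plan says.** Design and Methods describes the control as follows: "The sham device will be identical in appearance to the active device but will have no electrical current". It also promises that "Both providers and patients will be blinded to treatment allocation throughout the study". Blinding and Randomization extends the blind to all research coordinators, investigators and nurses apart from the unblinded lead coordinator, the person dispensing devices and the biostatisticians.

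Item 4 of the NSS-2 BRIDGE placement details sets out the advice given before placement: "The patients will be advised that they may feel a slight pulsing sensation and perhaps a warming sensation in the ear". The same item continues: "The pulsing and warming sensation may disappear after approximately 5 minutes". It also allows an array to be repositioned if discomfort increases.

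The primary variable is the change in COWS from baseline to one hour (Primary Efficacy Variable). Background and Rationale describes COWS as a mix of subjective symptoms and objective signs. On who scores it, the Safety Monitoring Plan says: "COWS score ratings will be filled out by nursing staff or provider as per standard of care".

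The allocation guess is described twice. Data Collected says that, upon completion of device treatment, "patients will be asked if they thought they had an active or inactive device". Item 9 of the Efficacy Information list reads: "Whether the patient thinks they had an active or inactive device at end of 5 days treatment". The end-of-treatment questions are to be analysed descriptively. No guess is planned at one hour.

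**The concern.** A device without current cannot produce electrical pulsing. A sham patient who has been told that pulsing is possible, and who never feels any, has a cue about allocation within minutes of placement. An active patient who does feel it has the opposite cue. Nothing in item 4 says that absence of sensation is uninformative, and nothing asks patients not to mention sensations to whoever scores COWS.

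The primary score follows at one hour and rests partly on what the patient reports, such as anxiety, aches, nausea and craving. If belief about allocation differs between arms and shifts those items, the t-test cannot tell that shift from a device effect.

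The planned guess does not settle the matter. By the time it is asked, buprenorphine has been started (at one hour) and several days of symptom course have followed. The answer mixes early sensation with later experience. The trial report would have no evidence, in either direction, on belief when the primary endpoint was scored.

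**Working it through.** **Inputs from the Power Calculation section.** 25 per arm, two-sided t-test, final alpha 0.049, SD about 6 COWS points, detectable difference 0.94 SD (stated as about 5.7 points), power at least 90%.

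**The plan's own figure.** The noncentral t with 48 degrees of freedom gives 90.1% power at 0.94 SD. The stated power reproduces.

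**Scale of the test.** The standard error of the difference is 6 × √(2/25) = 1.697. The critical t is 2.020. The smallest observed difference that reaches significance is 2.020 × 1.697 = 3.43 points.

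**Assumed inputs.** The documents give neither a correct-guess rate nor an effect of belief on COWS. Both are assumed here:
- b, the fall in COWS caused by believing one has the active device: 3 or 5 points, and 2 points as a weak case;
- the share guessing correctly: 70% or 80%, and 60% as a weak case;
- no true device effect.

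**Formula.** Let p_A and p_S be the shares of the active and sham arms who believe their device is active. The spurious difference is b × (p_A − p_S).
- Both arms guess correctly with probability g: p_A = g and p_S = 1 − g, so the bias is b(2g − 1).
- Only sham patients guess better than chance: p_A = 0.5 and p_S = 1 − g, so the bias is b(g − 0.5).

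The rejection probability is the noncentral t tail at noncentrality bias/1.697, for the final test at 0.049.

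| b | Correct | Bias, sham only | Type I error | Bias, both arms | Type I error |
|---|---|---|---|---|---|
| 3 | 70% | 3 × 0.2 = 0.6 | 6.3% | 3 × 0.4 = 1.2 | 10.5% |
| 3 | 80% | 3 × 0.3 = 0.9 | 8.0% | 3 × 0.6 = 1.8 | 17.8% |
| 5 | 70% | 5 × 0.2 = 1.0 | 8.8% | 5 × 0.4 = 2.0 | 20.9% |
| 5 | 80% | 5 × 0.3 = 1.5 | 13.7% | 5 × 0.6 = 3.0 | 40.7% |

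Weak case, both arms, 60% correct and b = 2: bias 2 × 0.2 = 0.4 points, type I error 5.5%.

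**Sensitivity to the SD.** If variation in belief adds to the SD of 6, the variance becomes 36 + b²g(1 − g). The four both-arms figures become 10.2%, 17.3%, 18.8% and 37.3%.

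**What a 1-hour guess could show.** If every patient guesses active or sham, the blinding index in one arm is 2p − 1, where p is the proportion correct. Its 95% half-width is 1.96 × 2√(p(1 − p)/25): 0.39 at p = 0.5, 0.36 at p = 0.7 and 0.31 at p = 0.8. That is enough to detect gross unblinding but not to rule out moderate unblinding.

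**The case against.** The plan is more careful than a quick reading suggests. The advice is hedged and the same for everyone, and it never ties sensation to the active device. The statement that sensation may disappear gives a sham patient an innocent reason for feeling nothing. Leads are placed percutaneously, so ear sensation need not be confined to the active arm. In the earlier neurostimulation trial summarised in the adverse-event section, ear discomfort was reported by three treated and three placebo patients. Staff other than those named are blinded. Consent pages are not available, so patients may be told more than item 4 records. COWS also includes objective signs, and a 5-point belief effect is close to the whole 5.7-point detectable difference.

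Most of this stands, and it rules out a stronger reading. A reader might infer that the advice provokes unblinding, or that the blind fails. The documents do not support that: they contain no data on how many patients feel pulsing or guess correctly, and a patient telling the rater is only a possibility. The discomfort counts do not settle the point the other way either, because they concern adverse events, not pulsing or guesses.

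The objection does not remove the gap. A patient who never felt anything still has a cue, since fading implies something felt first. Staff blinding does not stop a patient from describing sensations to the rater. A late guess remains uninformative about one hour.

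A further objection concerns the remedy. A 1-hour guess may itself reflect early benefit, given that the protocol expects a large effect within the hour. That is correct and limits its use. For the same reason the primary result split by guess, a post-randomisation variable, should not be used to draw conclusions. The COWS rater may also be the provider who chooses buprenorphine dosing, an analysed outcome, so asking that person to guess before dosing could do harm.

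**Conclusion.** The concern holds as a risk that the plan leaves open and does not assess at one hour, not as a demonstrated failure of the blind. The illustrated type I error runs from about 5.5% with weak unblinding, through about 6% to 14% if only sham patients guess better than chance, to about 10% to 41% if both arms do, against a nominal 4.9%. Every figure rests on the assumed guess rates and belief effects together with SD 6, 25 per arm and no true effect; none estimates what will happen in this trial. A reader might also infer that unblinding at one hour is impossible to measure. It is only unmeasured under the present schedule. Because belief at one hour cannot be recovered later and the change is nearly free, the plan should be amended.

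**What to change.** 1. In item 4, use one neutral text for both arms: some people feel pulsing or warmth and some feel nothing, any sensation may fade, and patients should not try to infer their device from it. Ask patients not to discuss ear sensations with the person scoring COWS. Problems with the device should still go to the medical provider, as item 4 already requires.

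2. Add one patient question (active, sham, don't know) after all 1-hour assessments are recorded and before buprenorphine. Keep the answer from the COWS rater and the dosing provider. Report it descriptively by arm, next to the Day 5 guess, which stays.

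3. State the limits in the analysis plan: the 1-hour guess may partly reflect early efficacy, 25 per arm can detect only gross unblinding, and the question may prime later self-reports of pain and craving. Do not ask the dosing provider to guess before dosing, and do not base conclusions on the primary result by guess.

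The cost is revised wording and one question per patient. Sample size, test and alpha are unchanged, and the primary score is already recorded when the question is asked.
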